### 12.66 Boosts to Metastatic Sites

Intracranial metastases can be boosted by any appropriate technique. Spinal metastases should be treated with a posterior field.

### 12.67 Field Shaping

Individually cut blocks to shape the skull field at the base of the skull and eye are strongly recommended. Similarly, field shaping may be required at the inferior border of the spinal field.

## 12.7 **Quality Review**

A retrospective quality review of radiotherapy planning and treatment will be performed by an independent radiologist.

## 13.0 **STATISTICAL CONSIDERATIONS**

This is a pilot study of concurrent carboplatin (CARBO), vincristine (VCR), and radiation therapy (XRT) followed by standard of care maintenance VCR and cyclophosphamide (CPM) ± cisplatin (CDDP) in children aged 3 to 25 years with metastatic medulloblastoma, high risk PNET and metastatic PNET. Eligible patients comprise those with supratentorial PNET and infratentorial PNET/MB with initial stage M1-M4 or >1.5cc residual tumor remaining after surgery and classical histology.

The primary objective of the protocol and the statistical analysis is to obtain preliminary estimates of event free survival (EFS) and to demonstrate less decrement in intellectual function in preparation for a future Phase III randomized trial including these treatments.

Statistical considerations for the primary objective are addressed below.

### 13.1 **Patient Accrual**

The Neuro-Oncology Program at Children's Hospital Colorado has seen an average of 5 patients per year with metastatic medulloblastoma, high risk PNET and metastatic PNET. We expect to enroll 10

patients. The current standard of care CCG 9961 was based on a pilot study of 10 patients (Goldwein et al, 1996).

## **13.2 Study Duration**

We originally anticipated that it would require approximately 24 months to complete accrual to this study. However, at this time we are more accurately anticipating to complete enrollment by 2016.

## **13.3 Study Endpoints**

### **13.31 Efficacy Endpoints**

**Event-free survival:** Minimum time to disease progression or recurrence, time to death for any reason, or time to occurrence of a second malignant neoplasm (SMN).

**Overall Survival:** Time to death from any cause.

**Intellectual Competence:** Performance is as good as or better than patients treated on CCG 9961 when adjusted for baseline performance

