We therefore propose extending the benefits of reduced dose craniospinal radiation to metastatic medulloblastoma patients and high-risk, non-metastatic supratentorial PNET patients, and metastatic PNET patients by adding the concurrent carboplatin to the reduced dose radiation. Data regarding neuropsychologic outcome in children treated for non-metastatic medulloblastoma, with 36 Gy craniospinal radiation, and the same maintenance chemotherapy (Packer et al, 2006) is available, and will serve as a control group to assess the benefit of a reduced radiation dose.

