- Short Form. This must state that the **elements** of consent have been presented orally to the subject and it must be in the language the subject is fluent in. A template of the Short Form is available in a variety of languages on the COMIRB web site under Forms. The subject or their representative and the witness, who in most cases is the translator, must sign this form. Consent Summary. The COMIRB approved English language consent form can serve as

the consent summary. The person obtaining consent and the witness (translator) should sign this.

Health outcomes on all subjects will be studied, but only an English-speaking subset will be measured for neuropsychologic outcomes due to the limitations of the testing measures used in this study in order to compare to the control group.

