# Post-op MRI should be done within 72 hours of surgery. For patients who undergo stereotactic biopsy only, post-op MRI is not required. Spinal MRI is required within 28 days of surgery if done post-operatively and within 7 days of surgery if done pre-op. (If MRI scan is performed within 7 days prior to surgery, then only a post-contrast examination is required). A pre-operative spinal MRI scan is preferable for patients with posterior fossa tumors because surgically-induced inflammation/blood can be difficult to distinguish from tumor.

% If counts are low, CBC should be performed twice weekly.

@ Ventricular CSF (either pre-or post-op) may be used only if a post-operative spinal tap is contraindicated. If a spinal tap is contraindicated and there is no ventricular CSF available, then CSF cytology can be waived for patients with supratentorial tumors or if there is documentation of spinal subarachnoid metastases (M3).

\*See Appendix 1 for neurological exam guidelines and Appendix 2 for Karnofsky/Lansky performance scales.

! Baseline neuropsychologic testing will be done between 3 – 6 months post-radiation, as was done on the 9961 protocol . An abbreviated battery will be utilized. See Appendix 3 for testing protocols.

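### Section 13.0 sets out to demonstrate less intellectual decrement, but the 13.31 criterion is met by a tie with CCG 9961, and the protocol does not make clear whether that comparator supplies a dose contrast

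*Protocol*

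**What the plan says.** Section 13.0 gives the primary objective of the protocol and its analysis as "to obtain preliminary estimates of event free survival (EFS) and to demonstrate less decrement in intellectual function". For EFS the aim is estimation; for intellectual function it is a directional demonstration.

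Section 13.31 lists intellectual competence as an efficacy endpoint and defines it in one line: "Performance is as good as or better than patients treated on CCG 9961 when adjusted for baseline performance". It gives no margin and does not state the comparator's dose.

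Section 3.0 (final paragraph) describes the neuropsychologic control data as coming from "children treated for non-metastatic medulloblastoma, with 36 Gy craniospinal radiation, and the same maintenance chemotherapy" and says that these data "will serve as a control group to assess the benefit of a reduced radiation dose". It does not name CCG 9961.

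Three other places bear on the comparator:

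- Section 4.3 (Non-English Speaking Subjects) says "only an English-speaking subset will be measured for neuropsychologic outcomes", because of limits in the "testing measures used in this study in order to compare to the control group".
- The footnote to the 6.1 table sets baseline testing at 3 to 6 months after radiation, "as was done on the 9961 protocol". Appendix 3 gives the same window.
- Section 13.1 says "The current standard of care CCG 9961 was based on a pilot study of 10 patients". The publication cited there is the one that 3.0 describes as treating 10 young children with reduced craniospinal radiation; 3.0 gives no Gy value for it.

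**The concern.** Limiting cognitive harm is the reason given for lowering the craniospinal dose. The objective asks whether patients lose less, whereas the criterion accepts patients who do equally well. An analysis written to 13.31 would take over the mismatch, and a tie could be reported as meeting part of the primary objective.

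What a tie means depends on what the controls received. Against 36 Gy controls, it leaves the hoped-for benefit undemonstrated. Against controls given a reduced dose, parity is a reasonable benchmark, but the comparison has little or no dose contrast and cannot assess what 3.0 says it will assess. The protocol does not say clearly which case applies.

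This is not detail that would normally wait for a statistical analysis plan. The protocol states both the objective and the criterion, and they do not agree.

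**Working it through.** **Step 1: objective against criterion.** Let D be the baseline-adjusted mean score of trial patients minus that of controls. The aim in 13.0 corresponds to D > 0. The criterion in 13.31 is met when D ≥ 0. D = 0 meets the second and not the first, so meeting 13.31 does not establish the objective.

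**Step 2: which dose did the comparator receive?** No section states the CCG 9961 craniospinal dose.

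- Suggesting that the control group in 3.0 is CCG 9961: 13.31 names that study, the 6.1 footnote copies its baseline timing, and 4.3 speaks of a single control group.
- Suggesting 36 Gy: 3.0 gives that dose for its control group. In addition, 13.1 calls CCG 9961 the current standard of care, and 1.0 puts standard-of-care dosing at 36 Gy (in describing this trial's population).
- Suggesting a reduced dose: 13.1 derives CCG 9961 from the 10-patient pilot, and 3.0 says that the pilot used reduced craniospinal radiation.

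Three readings follow:

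| Reading | What a tie on 13.31 means | What needs editing |
|---|---|---|
| Controls are CCG 9961 at 36 Gy | Benefit not demonstrated | 13.31 and 13.0 |
| Controls are CCG 9961 at a reduced dose | Coherent benchmark, little or no dose contrast | 3.0 and 13.0 |
| The 3.0 group and CCG 9961 are different cohorts | 13.31 does not test the contrast described in 3.0 | Label both cohorts and say which one serves 13.0 |

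If the controls had 36 Gy, the contrast is 36 − 23.4 = 12.6 Gy on the 12.531 figure, or 36 − 24 = 12 Gy on the 1.0 figure.

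**Step 3: what baseline adjustment removes.** Baseline is measured 3 to 6 months after radiation (6.1 footnote, Appendix 3). Adjusting for it compares change from that point on. Any loss before then is in the baseline score and is not counted as decrement.

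**Step 4: precision, as illustration only.** The protocol gives about 10 patients (4.2, 13.1), with only English speakers tested (4.3). It gives no SD, effect size, margin or power for this endpoint, so there is no plan figure to reproduce. Assumptions: 6 to 10 tested, SD of the adjusted score 10 to 15 points, control mean known without error.

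Half-width of the 95% interval = t(0.975, n−1) × SD/√n:

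- n = 10: 2.262/√10 = 0.715 SD, giving 7.2 points (SD 10) to 10.7 (SD 15)
- n = 8: 2.365/√8 = 0.836 SD, giving 8.4 to 12.5
- n = 6: 2.571/√6 = 1.049 SD, giving 10.5 to 15.7

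Probability that the interval lies wholly above zero (noncentral t, noncentrality = true benefit × √n/SD), from the least favourable case (n = 6, SD 15) to the most favourable (n = 10, SD 10):

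- true benefit 5 points: 10% to 29%
- true benefit 10 points: 26% to 80%

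Allowing for control error with an assumed 50 controls (pooled two-sample t), the half-width runs from 6.9 to 13.0 points. Power is 12% to 29% for 5 points and 33% to 81% for 10 points. The picture is the same.

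**The case against.** The strongest objection concerns the comparator. Section 3.0 never names CCG 9961, and 13.31 never states a dose. Section 13.1 says only that CCG 9961 was based on the pilot, in a section about accrual where the pilot serves as precedent for enrolling 10 patients; that does not establish that the dose carried over. A reader might infer that the protocol contradicts itself on the CCG 9961 dose, or that 3.0, 13.0 and 13.31 cannot all stand on any reading. The text does not support either inference. The chain rests on unstated steps, the standard-of-care wording in 13.1 and 1.0 can be read as pointing to 36 Gy, and the cohorts may simply differ. What remains is that the dose contrast is unclear. If the cohorts do differ, 13.31 still does not test the contrast in 3.0.

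A reader might also infer that a tie would show the dose reduction brings no cognitive benefit. It would only fail to demonstrate one. The 3.0 controls had non-metastatic disease, whereas trial patients are metastatic or high-risk, receive carboplatin during radiation and may have boosts to metastatic sites.

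The precision figures rest on assumed inputs. They show no protocol figure to be wrong and are not needed for the mismatch.

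Finally, this is a pilot, and the hand-off rule (13.33) and closure rule (13.41) count deaths. No stated go or stop decision depends on this endpoint. That is correct and limits the consequence, but it does not remove a mismatch within a stated primary objective.

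**Conclusion.** The point holds in two parts of different strength. That the 13.31 criterion falls short of the 13.0 objective follows directly from the wording and needs no assumption: equal performance satisfies one and not the other. That the comparator's dose contrast is unclear is also supported, but any statement about what CCG 9961 patients actually received is an inference that the protocol cannot settle.

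The effect is on what may be concluded about cognition, not on whether the trial proceeds. Under the assumptions shown, an observed exact tie would be compatible with a true difference of roughly 7 to 16 points in either direction. That favours estimating over demonstrating, but it is illustration only. The point should be fixed; confidence is moderate because of the open comparator question.

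**What to change.** First reconcile 3.0, 13.1 and 13.31 by naming the neuropsychologic control cohort and the craniospinal dose it received. Then:

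- **If it is a 36 Gy cohort:** restate 13.31 as the baseline-adjusted difference from those controls with a 95% confidence interval, do not count parity as success for the smaller-decrement aim, and change the verb in 13.0 from demonstrate to estimate, in line with how the same sentence treats EFS.
- **If it received a reduced dose:** call the comparison a benchmark, drop the statement in 3.0 that it assesses the benefit of a reduced dose, and reword 13.0 to match.
- **In either case:** state in 13.31 that baseline is the test taken 3 to 6 months after radiation, so the comparison covers change after that point only.

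The cost is wording in 3.0, 13.0, 13.1 and 13.31, with no new patients or data. The downside is a more modest claim: the cognitive part of the objective becomes an estimate with an interval, or a benchmark, instead of a demonstration.

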continuous infusion Carboplatin at a dose of 30 mg/m^2/day for either 14 or 21 days during radiation therapy to head and neck cancer patients. Only the patients who had carboplatin for 21 days had leukopenia and thrombocytopenia. There were no serious infections. Six of twelve patients developed mucositis, none requiring interruption of treatment (Ausili-Cefaro et al, 1995). A Phase I study of bi-weekly Carboplatin during radiation therapy for children with brain stem gliomas showed a mean tolerated dose of 280 mg/m^2/week for seven weeks (Allen et al, 1995).

Craniospinal irradiation has improved the survival rates for medulloblastoma, but it has also been implicated in poor quality of life related to impaired cognitive functioning that worsens over time (Packer, 1989). Radcliffe et al showed that whole-brain radiotherapy decreases IQ. Age is inversely correlated with loss of IQ. Children younger than 7 at diagnosis showed a significant loss of IQ points (Radcliffe et al, 1992).

Ribi, et al, (Ribi et al, 2005) followed 51 children who were consecutively diagnosed with medulloblastoma. Only two of the patients did not receive radiation because they were less than 3 years old. The other children received between 23.4-36.0 Gy craniospinal irradiation and with a boost of 48.0-55.0 Gy irradiation to the tumor bed. Significant deficits in neurocognitive functioning were seen in all of the patients. They had concurrent endocrine deficits (61%), neurological complications (72%), and significant school problems (72%)

Reduced dose craniospinal radiation has been shown to decrease the cognitive deficits. Mulhern et al demonstrated, in 22 children with medulloblastoma, that less severe neuropsychologic injury occurred when treated with only 23.4 Gy instead of 36 Gy craniospinal radiation. Once again, age was correlated with toxicity, with older children experiencing fewer cognitive deficits than younger children (Mulhern et al, 1998).

Goldwein, et al, treated 10 children diagnosed with medulloblastoma between 18 and 60 months of age with reduced craniospinal radiation . The patients received reduced dose craniospinal

radiation, a radiation boost to the tumor bed and standard maintenance chemotherapy. Survival at over 6 years was 70%, which is the accepted national survival rate for medulloblastoma with 36 Gy craniospinal radiation. The survivors had minimal neurocognitive damage, but did have decreased growth rates (Goldwein et al, 1996).

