## **4.0 METHODS**

### **4.1 Eligibility Criteria**

#### **Inclusion Criteria**

- Age greater than 3 years and less than 25 years.
- Patients with one of the following diagnoses by histological diagnoses and by head and spine MRI:
  - Classic histology metastatic medulloblastoma
  - Desmoplastic histology metastatic medulloblastoma
  - High-risk supratentorial, non-metastatic, PNET
  - Metastatic PNET
- Newly diagnosed patients who have not received prior therapy, with the exception of one short course of emergent chemotherapy in newly presenting patients with neurological compromise per provider decision
- Only patients who are expected to survive at least 6 weeks will be eligible for this study.

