#### 12.532 Primary Site Boost

All patients with primary tumor in the posterior fossa will receive a boost of 32.4 Gy to the posterior fossa. All patients with a supratentorial primary tumor will receive a boost 32.4 Gy to the volume described in section 12.3. As noted there, the total dose to the optic chiasm and both optic nerves should be limited to 50.4 Gy. In addition, if the boost volume occupies more than 2/3 of the supratentorial compartment, the boost dose should be limited to 27 Gy.

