#### 12.533 Metastatic Site Boost

Patients with M1 disease will receive no additional boost. Patients with M2 disease (intracranial subarachnoid disease) will receive boosts of 32.4 Gy to focal areas of supratentorial or posterior fossa metastatic disease. If the volume of a boost to the supratentorial compartment exceeds 2/3 of the

supratentorial compartment volume, the boost will be limited to 27 Gy. The boost dose to the optic chiasm and both optic nerves must be limited to 27 Gy. 3D treatment planning may be used for boosting M2 disease. If 3D planning is used, definitions boost volumes for M2 disease will be the same as specified for boosts to the primary tumor. Patients with M3 disease (spinal deposits of disease) are subdivided into those with diffuse disease and those with focal disease. Diffuse spinal disease is defined as radiographically visible multiple sites of disease in each of at least 3 out of 4 spinal regions (i.e., cervical, thoracic, lumbar or sacral).

If there is diffuse involvement of the spine, the entire spine will be treated to 23.4 Gy. An MRI scan of the spine should be performed when the spine has received 23.4 Gy, and areas of visible disease remaining at that point should be boosted to 45 Gy when above the termination of the spinal cord and 50.4 Gy when below the termination of the cord. If there are focal areas of spinal deposits which do not meet the definition of diffuse involvement defined above, the entire spine will be treated to 23.4 Gy. The focal areas of tumor seen on the initial spinal MRI will be boosted to 45 Gy. Focal deposits below the termination of the cord as defined by the initial MRI will be boosted to 50.4 Gy. The margin for boosting metastatic deposits will be at least 7 mm, and preferably 10 mm.

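### The CCG 9961 comparison in 13.31, adjusted for baseline score, leaves age at radiation and supratentorial boosts unaddressed and cannot be read as the effect of reduced craniospinal dose

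*Protocol*

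**What the plan says.** Section 13.0 of the protocol includes in its primary objective "to demonstrate less decrement in intellectual function". Section 13.31 turns this into an endpoint: "Performance is as good as or better than patients treated on CCG 9961 when adjusted for baseline performance". It names one adjustment variable and no matching or restriction.

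Section 3.0 describes the control data as coming from "children treated for non-metastatic medulloblastoma, with 36 Gy craniospinal radiation, and the same maintenance chemotherapy" and says that these data "will serve as a control group to assess the benefit of a reduced radiation dose". Section 3.0 does not call this group CCG 9961. I take it to be the same group because 13.31 names 9961 as the comparator and the footnote to the table in 6.1 aligns baseline testing with 9961.

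On what drives IQ loss, section 3.0 names whole-brain radiotherapy and age: "Age is inversely correlated with loss of IQ", with significant loss in children under 7. Eligibility in 4.1 is "Age greater than 3 years and less than 25 years".

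On dose, 12.531 gives 23.4 Gy to the craniospinal axis. Section 12.532 adds: "All patients with a supratentorial primary tumor will receive a boost 32.4 Gy to the volume described in section 12.3". Section 12.533 gives M2 patients "boosts of 32.4 Gy to focal areas of supratentorial or posterior fossa metastatic disease". Both lower the boost to 27 Gy when it would cover more than two thirds of the supratentorial compartment.

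**The concern.** The comparison is meant to show what a lower craniospinal dose does for later intellectual function. Two features can move the result for other reasons.

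The first is age at radiation, which the protocol itself treats as a determinant of loss. The second is the supratentorial boost. Section 3.0 places medulloblastoma in the cerebellum, so non-metastatic controls have no supratentorial primary or metastasis to boost, whereas the study enrols supratentorial PNET and M2 disease.

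A favourable result could therefore come from an older study group, and an unfavourable one from boosts that no control needed. The result is to inform a randomized Phase III proposal, so a wrong attribution would carry forward.

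**Working it through.** **Reproducing the plan's dose figures.** 23.4 + 32.4 = 55.8 Gy, the prescribed dose in 12.31 and 12.34. 55.8 / 1.8 = 31 fractions, as in 5.1. The figures used below are therefore the plan's own.

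**Boost.** Let f be the boosted share of the supratentorial compartment. Ignoring dose fall-off outside the boost, mean supratentorial dose is 23.4 + 32.4f, or 23.4 + 27f above two thirds.

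| f | Boost (Gy) | Mean supratentorial dose (Gy) |
|---|---|---|
| 0.1 | 32.4 | 26.6 |
| 0.2 | 32.4 | 29.9 |
| 0.3 | 32.4 | 33.1 |
| 0.39 | 32.4 | 36.0 |
| 0.5 | 32.4 | 39.6 |
| 2/3 | 32.4 | 45.0 |
| just above 2/3 | 27 | 41.4 |
| 1.0 | 27 | 50.4 |

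The mean equals the controls' stated 36 Gy at f = (36 − 23.4) / 32.4 = 12.6 / 32.4 = 0.389. Three inputs move that point:

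- If the controls' posterior fossa boost adds s Gy to their mean supratentorial dose, the crossover is (12.6 + s) / 32.4, later by 1 / 32.4 = 0.03 per Gy.
- If the craniospinal dose is 24 Gy, as in 1.0, 2.0 and 5.1, it is 12 / 32.4 = 0.37. These sections and 12.531 need reconciling.
- If the controls' craniospinal dose was below 36 Gy, it comes earlier.

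**Age.** No figure in the protocol allows a bias to be calculated. By direction alone, older study patients would favour the regimen, younger ones would count against it, and equal ages would give no bias. For scale, assume SD 15 IQ points, baseline–outcome correlation 0.7, 100 controls and 10 study patients:

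- SE = 15 × √(1 − 0.49) × √(1/100 + 1/10) = 3.6 points.
- Bias = age slope × mean age difference. With 0.5 to 1.5 points per year and 2 to 6 years, it is 1 to 9 points in either direction.
- Read the criterion as a point estimate of zero or more (the protocol gives no margin). With no true difference, the chance of meeting it is 50% at equal ages, 61% to 99% if study patients are older, and 39% to 1% if they are younger.
- With a true deficit of 5 points, the chance is 8% at equal ages and 13% to 87% if study patients are older.

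All of these age inputs are assumptions.

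**Why baseline does not absorb either factor.** The table in 6.1 and Appendix 3 put baseline three to six months after radiation, with retesting at two and five years. Section 3.0 says impairment worsens over time. Age and regional dose act on the decline after baseline, so two patients with equal baseline scores can be expected to diverge if they differ in either.

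**The control dose.** Section 3.0 gives the controls 36 Gy. Section 13.1 says CCG 9961 grew out of a pilot of 10 patients, and section 3.0 describes that pilot as using reduced-dose craniospinal radiation. These statements do not sit together. If the controls were also treated at a reduced dose, the contrast shrinks or vanishes.

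**The case against.** Section 13.31 is a one-line endpoint, not a model, and an analysis plan, which I have not seen, may add covariates. Nothing in 13.31 forbids age. That is fair as far as it goes, but the protocol does more than leave a gap: it names a specific adjustment and, in 3.0, attaches a specific causal reading that the adjustment cannot carry.

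Three stronger readings are tempting, and the protocol does not support them:

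- A reader might infer from the upper age limit of 25 that study patients are older than the controls. No 9961 age range is given, 13.0 calls patients aged 3 to 25 children, and 3.0 puts the peak age at diagnosis at five.
- A reader might infer that boosts cancel the dose reduction in every boosted patient, or that the protocol names boost dose as a cause of IQ loss. It names whole-brain dose; the step to mean supratentorial dose is an inference, though 12.43 does list supratentorial brain for dose-volume review. Many boosts will be small, since 12.35 uses a 1 cm margin and M2 boosts are focal. Assuming a compartment of 800 to 1,200 cc and a spherical target, f = 0.39 is about 310 to 470 cc, a tumour of roughly 6.4 to 7.6 cm before surgery.
- A reader might infer that unboosted patients alone would give a clean dose comparison. They still differ from controls in concurrent carboplatin and metastatic stage.

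Tests suited to the patient's age (Appendix 3) deal with age at testing, not with vulnerability at the time of radiation.

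The objection that ten patients, English speakers only, cannot support much modelling stands. On the assumptions above, the 95% interval is already about ±7 points. This argues for matching, restriction and description, not for leaving the endpoint as it is.

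**Conclusion.** The point holds in a limited form. Adjusting for a baseline taken after radiation does not remove an age difference between the study and CCG 9961; whether one exists, and its direction, cannot be told from the protocol. Supratentorial boosts change cerebral dose in a way the controls would not share: they dilute the reduction at smaller volumes and reach or exceed the stated 36 Gy at about 39% of the compartment or more, if boost spill in controls is ignored and 36 Gy is correct. The two influences need not point the same way, so the net effect is unknown. Concurrent carboplatin and metastatic stage also separate the groups. The comparison can describe the whole regimen in a different population; it cannot isolate the effect of craniospinal dose.

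**What to change.** - In 13.31, make the comparison adjusted for or matched on age at radiation as well as baseline score, within the ages that 9961 covers. If only summary control data can be had, compare below 7 with 7 and above, the cut that section 3.0 uses.
- Report patients with and without a supratentorial boost separately and descriptively, using the supratentorial-brain dose-volume data that 12.43 already requires.
- State in 3.0 and 13.31 that the result describes the whole regimen in a different population and does not isolate the effect of craniospinal dose, because concurrent carboplatin and metastatic stage also differ.
- Before any dose contrast is claimed, reconcile the 36 Gy given for controls in 3.0 with 13.1 and the account of the reduced-dose pilot in 3.0.

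The cost is mainly wording and simple tabulation. The study's own ages and dose-volume data will be to hand. Section 3.0 says control outcome data are available but not whether ages come with them, so that must be checked. The price is fewer patients in each comparison and a more cautious conclusion.
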